4.2.2 Study Intervention Phase

Part 1: Enrolled healthy subjects will have the OsciPulse device applied by study or medical personnel according to the OsciPulse Instructions for Use. The subject will wear the device for a maximum of 3 hours while laying down. At the end of the study period the subject will receive an ultrasound scan of the deep venous system of the thigh/groin region to measure hemodynamics at a venous valve during immobility and during use of the OsciPulse device. Finally, the subject will participate in a questionnaire evaluation of their comfort and experience with the OsciPulse device. Participants will be compensated at \$50/ hour for their participation.

Part 2: After informed consent is obtained, baseline demographic and clinical data will be collected. The subjects will be randomized with equal allocation to either of the two treatment sequence groups:

- Group A (OsciPulse device then standard IPC device)
- Group B (standard IPC device then OsciPulse device)

For group A, the OsciPulse device will be applied to the subject on both legs in the first 3 hours. The subject will wear the device for the maximum number of hours as possible up to 3 hours. The [REDACTED] research team inquire with the subject if the device was removed during the testing period.. During the 3-hour period the study team will monitor for adverse events and a hemodynamic ultrasonography may be performed (when feasible) following the Ultrasound SOP. After 3 hours, the subject will complete the questionnaire evaluating the tolerability and safety of the device. In the following 3 hours, the standard IPC will be applied. Subjects will undergo the same procedure for compliance monitoring, adverse event monitoring, hemodynamic ultrasonography (when feasible), and questionnaire evaluation.

For group B, the same procedure will be performed but with the standard IPC in the first 3 hours and the OsciPulse device in the next 3 hours.

Participants will be compensated \$100 for their participation.

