8.5 Hemodynamic ultrasonography

A hemodynamic ultrasonography will be performed (when feasible) by certified technician/radiologist or physician trained in venous valve sinus imaging. The study specific ultrasound procedure SOP will be followed. All efforts will be made to conduct the ultrasound procedure with the assigned device even if subject is no longer clinically wearing the assigned device but agrees to wear for ultrasound procedure.

The following parameters will be measured both at rest and during the inflation period of the OsciPulse device and the calf ICD: centerline flow velocity, centerline flow, [REDACTED]

Video clips of the 2D color Doppler exams will be collected by the imaging personnel and transferred via a data storage device to [REDACTED] study personnel. The data will then be blinded and sent to Dr. [REDACTED], an expert in ultrasound image quantification, to perform the analysis and quantify the above parameters which will be provided back to the [REDACTED] team for data entry.

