9.2.4 Statistical Methods

The statistical approach to analysis will be to use paired t-tests to evaluate the difference between the standard of care cleared intermittent pneumatic device and the OsciPulse device using a

paired t-test. We will evaluate the primary endpoint of tolerability through quantification of the difference between the visual analog scale markings on the patient questionnaire for each device. We will also use a paired t-test to evaluate the changes in venous flow that occur in each patient during use of both devices.

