9.2.6 Efficacy Analysis

Efficacy will be scored by the ultrasound measurements of venous blood flow during the use of the OsciPulse device and reference therapy device. Ultrasound measurements during device action will provide quantification of centerline venous flow velocity, the amount of flow within the sinus of the valve at the sapheno-femoral junction, and the amount of reversing flow in the sinus of the sapheno-femoral junction valve. Measurements may be taken at other vascular sites if the visualization window is not of sufficient quality for data collection at the sapheno-femoral junction. These measurements will be compared for each device and difference for each individual patient will be quantified and a paired t-test will be used to evaluate the overall efficacy.

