If in the judgment of, the sponsor, the IRB/IEC, and/or the investigator, the amendment to the protocol substantially changes the study design and/or increases the potential risk to the subject and/or has an impact on the subject's involvement as a study participant, the currently approved written informed consent form will require similar modification. In such cases, informed consent will be renewed for subjects enrolled in the study before continued participation.

The table below is intended to capture changes of IRB-approved versions of the protocol, including a description of the change and rationale.

Version	Date	Description of Change	Brief Rationale
V1	2020	Original Protocol	

Version	Date	Description of Change	Brief Rationale
V2	02 Feb 2021	Updated background information, clarified randomization procedures, updated vulnerable populations section, clarified monitoring procedures prior to moving to part 2, clarified SAE reporting procedures. Other minor and administrative changes for clarity and completeness.	To provide most current and accurate information.
V3	21 Apr 2021	Updated AE grading criteria to align with CTCAE definitions, as planned for use.	To align with CTCAE dictionary planned for use.
V4	01 Sep 2021	Updated applicable sections to clarify that ultrasound procedures will be completed when feasible	To account for variability in the availability of ultrasonographers during study procedures.
V5	12 Jan 2022; addl updates 17 Feb 2022	Updated eligibility criteria for Part 2, device description. Included description of video consenting process.	To facilitate recruitment and provide more current description of device. To provide accurate description of consenting process.
V6	01 Jun 2022	Updated eligibility criteria for Part 2, update study duration for Part 2, Removed requirement for physical examination, Updated procedure for compliance monitoring.	To facilitate recruitment and increase the frequency of subject's completing the study. To update study procedures based on the reduced study time.

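### The flow comparison discards every subject scanned on only one device; analysing all readable scans is a cheap but modest gain on a secondary endpoint

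*Combined protocol and SAP*

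**What the plan says.** Sections 9.2.2, 9.2.4 and 9.2.6 give one method for flow. Section 9.2.4: "We will also use a paired t-test to evaluate the changes in venous flow". Section 9.2.6: "difference for each individual patient will be quantified and a paired t-test will be used to evaluate the overall efficacy". No method is given for a subject with a scan on one device only.

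The scans are conditional. Section 4.2.2 says that within a 3-hour period "a hemodynamic ultrasonography may be performed (when feasible) following the Ultrasound SOP", and the second period follows the same procedure. The schedule in section 7, sections 7.3.2 and 7.3.3, and section 8.5 ("A hemodynamic ultrasonography will be performed (when feasible) by certified technician/radiologist") carry the same condition. The amendment history in 11.6 gives the reason for it: "To account for variability in the availability of ultrasonographers during study procedures". Section 8.5 limits one cause of missing scans: "All efforts will be made to conduct the ultrasound procedure with the assigned device even if subject is no longer clinically wearing the assigned device".

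Section 9.3 names a single analysis population. It requires exposure to both devices, the questionnaires and the ultrasound examinations, and it leaves out everyone who does not complete the protocol requirements.

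**The concern.** The plan foresees missing scans but analyses only complete pairs. Flow is a stated secondary objective (3.2) and the whole of the efficacy analysis (9.2.6). The sample is 15 to 20 subjects, and the only allowance for losses, in 9.2.3, concerns tolerability and safety data. Nothing protects the number of scan pairs. If many subjects are scanned once, the device comparison rests on few pairs while usable scans are set aside. The rule for single scans should also be fixed before anyone sees how many there are.

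**Working it through.** **The plan's own figure.** Section 9.2.3 allows 6 losses from 20: 20 − 6 = 14 with tolerability and safety data. This reproduces. No sample size, power, SD or correlation is given for flow, so there is no flow figure to reproduce. I use N = 15, the evaluable minimum in section 5.5.

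**Assumed inputs (none is in the documents).**
- p, the probability that a given scan is feasible: 0.5 to 0.9.
- φ, the correlation of feasibility between a subject's two periods: 0, 0.5, 0.8.
- ρ, the within-subject correlation of the flow measure: 0.3 to 0.9.
- SD 1 on each device, and single scans split evenly between devices.

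**Counts.** Expected pairs n = N[p² + φp(1 − p)]. Expected once-scanned subjects 2m = 2N(1 − φ)p(1 − p), that is, m per device.

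**Variance of the device difference.** Pairs only: 2(1 − ρ)/n. All scans, by generalised least squares: 2/[n/(1 − ρ) + m]. The proportional fall in standard error (SE) is 1 − 1/√[1 + m(1 − ρ)/n]. Expected counts are put into these formulas, so the results are approximate. A period term leaves them unchanged when sequences and single scans are balanced.

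**Worked case: p = 0.7, φ = 0, ρ = 0.5.** n = 15 × 0.49 = 7.35; 2m = 15 × 2 × 0.21 = 6.30, so m = 3.15.
- SE from pairs only: √(1/7.35) = 0.369.
- SE from all scans: √[2/(14.70 + 3.15)] = 0.335, a fall of 9.3%.
- SE if all 15 had both scans: √(1/15) = 0.258.

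Missing scans cost 0.369 − 0.258 = 0.111. The model recovers 0.369 − 0.335 = 0.034, about 31% of that.

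**Range (N = 15).**

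| φ | p | pairs | once-scanned | SE fall, ρ=0.3 | ρ=0.5 | ρ=0.7 | ρ=0.9 |
|---|---|---|---|---|---|---|---|
| 0 | 0.5 | 3.75 | 7.50 | 23.3% | 18.4% | 12.3% | 4.7% |
| 0 | 0.7 | 7.35 | 6.30 | 12.3% | 9.3% | 5.9% | 2.1% |
| 0 | 0.9 | 12.15 | 2.70 | 3.7% | 2.7% | 1.6% | 0.6% |
| 0.5 | 0.5 | 5.63 | 3.75 | 10.0% | 7.4% | 4.7% | 1.6% |
| 0.5 | 0.7 | 8.93 | 3.15 | 5.7% | 4.1% | 2.5% | 0.9% |
| 0.5 | 0.9 | 12.83 | 1.35 | 1.8% | 1.3% | 0.8% | 0.3% |
| 0.8 | 0.5 | 6.75 | 1.50 | 3.7% | 2.7% | 1.6% | 0.6% |
| 0.8 | 0.7 | 9.87 | 1.26 | 2.2% | 1.6% | 0.9% | 0.3% |
| 0.8 | 0.9 | 13.23 | 0.54 | 0.7% | 0.5% | 0.3% | 0.1% |

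**Estimated variances.** The formulas treat ρ as known. Simulated REML fits give slightly smaller gains. With 10 pairs and 4 single scans, the fall is 5.3%, 3.7%, 2.4% and 0.4% for ρ = 0.3, 0.5, 0.7 and 0.9, against 6.3%, 4.7%, 2.9% and 1.0% from the formula. In simulation with independent feasibility, power rose by about 2 to 9 percentage points and type I error stayed near 5%, even when one device's SD was three times the other's.

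**What missing scans cost.** The 95% CI half-width of the paired comparison, in SDs of the difference, is t(0.975, n − 1)/√n: 0.58 with 14 pairs, 0.72 with 10, 0.84 with 8 and 1.05 with 6.

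**The case against.** The strongest objection is that a paired t-test on complete pairs is valid and standard. Its within-patient differences also remain sound when the chance of a scan depends on stable features of the patient. Single scans add only between-subject information, which is weaker and rests on more assumptions. This stands: the mixed model is an improvement in efficiency and does not correct an error. A reader might infer from the discarded scans that the planned test is biased or wrong; nothing in the documents supports that.

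The second objection concerns size. A reader might treat the two scans as independently feasible and take the upper end of the range. The documents do not say that they are independent. Both scans fall in one 6-hour session at one site, and the stated cause is sonographer availability, so they may well succeed or fail together. Fewer subjects are then scanned once, and the gain shrinks. The effort in section 8.5 to scan even after a device has come off removes one further cause. This objection also stands, which is why φ is varied above.

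Third, the test is not the only thing that drops these subjects: 9.3 does so as well, so editing 9.2.4 alone would create a contradiction. This stands and shapes the fix.

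Fourth, 9.2.6 allows other vascular sites when the view is poor. A single scan at another site mixes site with device, whereas a pair taken at one site cancels it. This too stands and needs a rule.

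Unequal variance between devices was also considered. It does not defeat the proposal, given the simulated type I error.

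**Conclusion.** The point holds as a minor one on a secondary endpoint, in a convenience sample with no power target. The paired test and 9.3 together discard every once-scanned subject, in a plan that makes each scan optional.

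For 15 subjects and feasibility of 0.5 to 0.9, the recoverable fall in standard error is about 2-23% with independent feasibility and ρ from 0.7 to 0.3. It is about 1-10% with feasibility correlation 0.5, and under 5% with feasibility correlation 0.8 or ρ of 0.9. All three inputs are assumptions. A reader might infer that a different test would restore the precision lost to missing scans. It would not: in the worked case it recovers about a third of the loss. If nearly all subjects get both scans, the results barely change.

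**What to change.** - **9.2.2, 9.2.4, 9.2.6:** analyse each flow parameter with a linear mixed model on every readable scan, subject to the imaging-site rule below. Use device and period as fixed effects, subject as a random effect, and Kenward-Roger degrees of freedom.
- **Reporting:** give the device difference with its 95% CI, the number of pairs and of single scans by device and period, and the reasons for missing scans.
- **Sensitivity analysis:** keep the paired t-test on complete pairs.
- **9.3:** define a separate flow population of subjects with at least one readable scan, so that the model does not contradict the analysis set.
- **Imaging site:** admit single scans only from the sapheno-femoral junction, or adjust for site.

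The cost is SAP wording and a few lines of code, with no new data and no burden on patients. The downside is that the model assumes missing scans are unrelated to the flow they would have shown. That is plausible if sonographer availability is the cause, but not assured; the paired analysis serves as the check.

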9.2.5 Baseline Data

Baseline and demographic characteristics will be summarized by standard descriptive statistics (including mean and standard deviation for continuous variables such as age and standard percentages for categorical variables such as gender).

9.2.6 Efficacy Analysis

Efficacy will be scored by the ultrasound measurements of venous blood flow during the use of the OsciPulse device and reference therapy device. Ultrasound measurements during device action will provide quantification of centerline venous flow velocity, the amount of flow within the sinus of the valve at the sapheno-femoral junction, and the amount of reversing flow in the sinus of the sapheno-femoral junction valve. Measurements may be taken at other vascular sites if the visualization window is not of sufficient quality for data collection at the sapheno-femoral junction. These measurements will be compared for each device and difference for each individual patient will be quantified and a paired t-test will be used to evaluate the overall efficacy.

9.2.7 Safety Analysis

All subjects entered into the study and randomized at the baseline visit will have detailed information collected on adverse events for the overall study safety analysis

9.3 Subject Population(s) for Analysis

We will analyze the Protocol-compliant population defined as any subject who was randomized and received the protocol required investigational product exposure, the reference therapy product exposure, and completed the required questionnaires and ultrasound examinations. Subjects who are enrolled but do not complete the protocol requirements will not be analyzed.

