5.5 Total Number of Subjects and Sites

Part 1: Recruitment will end after 3 subjects have been enrolled.

Part 2: Recruitment will end when no fewer than fifteen (15) evaluable subjects and no greater than twenty (20) evaluable subjects have completed the clinical protocol. In the event a subject begins the clinical protocol, however, does not meet protocol defined requirements of "evaluable" status (see section 9.2, Part 2), the Sponsor reserves the right to replace that subject, which may result in greater than twenty (20) subjects being enrolled. In the unlikely event a disproportionate number of enrolled subjects do not meet the protocol defined requirements for reaching "evaluable" status, the Sponsor may pause the study to enrollment to reevaluate recruitment, inclusion and/or exclusion, or any other activity deemed necessary at the time.

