9 STATISTICAL PLAN

9.1 Part 1

Part 1 of the trial is designed to test the tolerability of the OsciPulse system on healthy subjects for 3 hours prior to the 6-hour trial on patients. This is to determine if there are any immediate comfort issues that can be addressed prior to use in the clinical setting. Healthy volunteers are not the target population for the OsciPulse device and will have different tolerability for discomfort than hospital patients, but we feel that this test will be a qualitative analysis of the product prior to use in the target population. Subjects will indicate if the device caused 1) no discomfort, 2) mild discomfort, or 3) significant discomfort. **We will require that all three subjects indicate that there was not “significant discomfort” as reported on the subject questionnaire before continuing to Part 2.** This will be confirmed by the monitor prior to continuation to Part 2.

9.2 Part 2

Part 2 of the trial is designed to assess the tolerability and hemodynamic efficacy of the OsciPulse device in the clinical setting. The Primary endpoint is tolerability, which will be evaluated with questionnaires scored with a visual analog scale and will be directly compared between the OsciPulse device and a reference therapy device. Evaluable subjects will have completed the 6-hour study time that includes 3 hours with both therapies. This allows for the comparison between the therapies that makes the data quantitative rather than subjective. We will further measure hemodynamic efficacy through vascular ultrasound measurements of venous flow

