9.2.1 Primary Endpoint

The primary endpoint of this study is OsciPulse device tolerability compared to the current standard of care device. This endpoint will be measured by quantifying the differences in the responses to the questions on the subject questionnaire for each device. We will compare the visual analog scale ratings for the first 4 questions for each subject between the OsciPulse device and the reference therapy device. There are also 4 questions on the 6-hour questionnaire that ask the participants to directly compare the two devices, to determine the difference in tolerability. The ratings are reported in millimeters and the average differences between the responses will be statistically evaluated using a paired t-test.

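### Section 9.3 makes completed ultrasound a condition of analysis although Part 2 scans are optional, so subjects with complete primary VAS data could be excluded

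*Combined protocol and SAP*

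**What the plan says.** Section 9.3 names one population, with no distinction by endpoint. A subject must have been randomized, have received both devices, and have "completed the required questionnaires and ultrasound examinations". It closes: "Subjects who are enrolled but do not complete the protocol requirements will not be analyzed".

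Part 2 ultrasound is conditional wherever its performance is described. Section 4.2.2 says that "a hemodynamic ultrasonography may be performed (when feasible) following the Ultrasound SOP", and section 8.5 says "A hemodynamic ultrasonography will be performed (when feasible) by certified technician/radiologist". The Part 2 schedule (Figure 3), sections 7.3.2 and 7.3.3 and the study summary carry the same condition. The amendment history (11.6, V4) gives the reason: ultrasonographers are not always available.

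The primary endpoint in 9.2.1 comes from the questionnaire: "We will compare the visual analog scale ratings for the first 4 questions for each subject", compared between devices with a paired t-test. Ultrasound feeds the hemodynamic endpoints, which 9.2.2 lists as secondary.

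Section 9.2 sets out who is evaluable without mentioning a scan: "Evaluable subjects will have completed the 6-hour study time that includes 3 hours with both therapies". Section 5.5 uses that definition to end recruitment at 15 to 20 evaluable subjects and, for a subject who is not evaluable, says "the Sponsor reserves the right to replace that subject". Section 9.2.3 allows for 6 losses among 20 enrolled and expects 14 with usable tolerability and safety data. Section 9.2.7 bases the safety analysis on all randomized subjects.

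**The concern.** The plan expects some scans to be missing, yet lists scans among the conditions for being analysed at all. A measurement that the primary endpoint does not need can therefore remove a subject from the primary comparison.

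The recruitment rule does not protect against this. A subject with both device periods and both questionnaires but without a scan is evaluable under 9.2, counts towards the target in 5.5 and triggers no replacement. Recruitment could end at 15 evaluable subjects with fewer than 15 in the primary test.

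The loss may also not be neutral. Under 8.5, efforts are made to scan with the assigned device "even if subject is no longer clinically wearing the assigned device but agrees to wear for ultrasound procedure". A subject who stopped wearing a device and declines to put it back on has no scan with it. A scan condition could then select on tolerability, which is the outcome under test. The documents do not show the direction or size of any such shift.

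Finally, Part 2 is unblinded (6.6). If 9.3 can be read in two ways, the choice between two primary samples could be made after the responses are known.

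**Working it through.** **1. The plan's own count.** Section 9.2.3: 20 − 6 = 14, which reproduces. The losses it names are discharge, unexpected surgery, loss of consciousness and death. Missing scans are not among them.

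**2. One subject, four rules.** Take a randomized subject who completes 3 hours on each device and both questionnaires, but has no scan in one period.

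| Section | Status of this subject |
|---|---|
| 9.2 and 5.5 (evaluable, recruitment, replacement) | Counted; no replacement triggered |
| 9.2.1 (primary VAS) | All data present |
| 9.2.7 (safety) | Included, as randomized |
| 9.3 (analysis population), read literally | Not analysed |

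**3. Expected number analysed.** Let f be the share of evaluable subjects with scans on both devices. The documents do not give f, so it is an assumption. Expected number = n × f.

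| f | From 15 (minimum in 5.5) | From 14 (9.2.3) |
|---|---|---|
| 1.0 | 15 | 14 |
| 0.9 | 13.5 | 12.6 |
| 0.8 | 12 | 11.2 |
| 0.6 | 9 | 8.4 |
| 0.5 | 7.5 | 7.0 |

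If scans are missing independently with f = 0.9, the chance that at least one of 14 evaluable subjects is excluded is 1 − 0.9^14 = 0.77.

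**4. Effect on precision.** The 95% half-width for a mean paired difference is k(n) × SD, with k(n) = t(0.975, n − 1)/√n. The SD of the paired difference is not in the documents; 15, 25 and 35 mm are assumed.

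| n | k(n) | Width relative to n = 15 | Half-width in mm, SD 15 / 25 / 35 |
|---|---|---|---|
| 15 | 0.5538 | 1.000 | 8.3 / 13.8 / 19.4 |
| 14 | 0.5774 | 1.043 | |
| 13 | 0.6043 | 1.091 | |
| 12 | 0.6354 | 1.147 | 9.5 / 15.9 / 22.2 |
| 9 | 0.7687 | 1.388 | 11.5 / 19.2 / 26.9 |
| 8 | 0.8360 | 1.510 | |
| 7 | 0.9248 | 1.670 | |

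The relative widths do not depend on the assumed SD.

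**5. Safety.** The last sentence of 9.3 excludes every enrolled subject who does not complete the protocol, while 9.2.7 includes everyone randomized. Section 4.6.1 makes safety part of the primary endpoint. This conflict does not depend on ultrasound.

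**The case against.** The strongest reply is that 9.3 can be read without conflict. The word required can govern the scans as well as the questionnaires. A scan that was not feasible was then never required, and the subject stays in. Sections 9.2 and 9.2.3, which say nothing of scans, suggest that this may have been the intention. The reading is tenable, but no section states it or exempts a subject whose scan was not feasible. At best the primary population is ambiguous, and that still needs correcting.

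The selection argument can fairly be called speculative. The only stated reason for missing scans is staffing, which has no evident link to tolerability, and the sentence in 8.5 is meant to rescue scans. The exposure condition in 9.2 and 9.3 already selects on tolerability to some extent. These points stand as limits: the scan condition opens a further route to selection, of unknown direction and size.

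It is also true that this is a convenience sample with no stated power or precision target, so no amount of widening breaches a criterion of the plan. Starting from 15 takes the minimum; 5.5 allows up to 20 evaluable, and 20 × 0.75 = 15 would still remain at f = 0.75. The figures are therefore illustrative.

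On safety, 9.2.7 can be read as the specific rule that overrides 9.3. That is reasonable, but 9.3 makes no exception.

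**Conclusion.** The concern holds. As written, 9.3 can exclude subjects with complete primary VAS data because an optional secondary measurement is missing. It disagrees with the evaluable definition used for recruitment and with the safety population in 9.2.7. It should be corrected because it decides who enters the primary analysis.

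The existence of the conflict rests on the text alone. Its size cannot be determined from the documents. If nearly all scans are obtained (f between 0.9 and 1), 0 to 1.5 of 15 subjects are lost and the interval widens by at most about 9% (n = 13). At an assumed 80% or 60%, 12 or 9 subjects remain and the interval is 15% or 39% wider. At 50% (7 or 8 subjects) it is 51% to 67% wider. No bias of known direction is claimed.

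**What to change.** Replace the single population in 9.3 with one set per purpose:

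1. **Tolerability and compliance:** randomized subjects with both device exposures and completed questionnaires for both devices, whether or not ultrasound was obtained.
2. **Hemodynamic:** subjects with usable scans on both devices. Report the number scanned on each device and the reason for each missing scan (not feasible, or subject declined).
3. **Safety:** all randomized subjects, with a cross-reference to 9.2.7.

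Limit the closing sentence so that failing the conditions of one set excludes a subject from that set only. Align evaluable in 5.5 and 9.2 with set 1, stating the exposure condition in the same terms in all three places, so that the recruitment count and the primary-analysis count agree.

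The cost is text edits to 9.3, 9.2 and 5.5, with no new data collection. The tolerability and hemodynamic analyses may then have different n, which must be reported. Because evaluable would now require both questionnaires, a few more subjects might need replacing. The change does not address subjects who stop a device before completing its questionnaire; they remain outside set 1, as they do now.
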